7.1.3 Health Outcomes endpoint

- Total healthcare costs from admission to discharge between treatment groups.

7.1.4 Exploratory Endpoints

- Change in serum cytokines including IL-1 α , IL-1 β , and ferritin levels, as well as other exploratory biomarkers drawn at the same time as LSALT peptide concentrations.
- Change in baseline antiviral immunoglobulins (IgG, IgM, and IgA) at EOS.

Additional measures may be added. Data will be analyzed for the modified intent-to-treat (mITT) and per protocol (PP) populations.

7.2 Pharmacokinetic Variables

Blood samples for determination of LSALT peptide concentrations and related metabolites (degradation products) and cytokines will be obtained at Baseline prior to initiation of drug, and at the mid-point of the 2-hour drug infusion and immediately following the end of the 2-hour infusion on Days 1, 3, and EOT. A single blood sample will be obtained at EOS for measurement of cytokines/biomarkers only.

7.3 Safety Assessment

Safety will be assessed by changes from Baseline in:

- TEAEs
- Clinical laboratory tests (Appendix 2)
- Vital signs including pulse rate, blood pressure, body temperature, respiration rate, body weight
- Physical examinations
- 12-lead ECG
- Radiologic findings.

Additional assessments may be conducted as considered appropriate. Clinical labs, vital signs, ECG measurements, and radiologic findings may be repeated if needed to corroborate or refute abnormal findings. Both the original and replicate assessments should be recorded in the eCRF.

7.3.1 Adverse Events

An adverse event (AE) is any untoward medical occurrence in a patient participating in a clinical trial. An AE can be any unfavorable and unintended sign, symptom, or disease temporally associated with the use of the study medication, whether or not considered related to the study medication. AEs will be collected from the initiation of treatment until 30 days following the final dose. Pre-existing known clinically significant conditions observed at screening should be recorded as medical history.

This definition also includes accidental injuries, reasons for any change in medication (drug and/or dose), reasons for re-admission to a hospital, or reasons for surgical procedures (unless for minor elective surgery for a pre-existing condition). It also includes adverse events commonly observed and adverse events anticipated based on the pharmacological effect of the study medication. Any laboratory abnormality assessed as clinically significant by the PI must be recorded as an adverse event.

A treatment-emergent adverse event (TEAE) is also defined as any adverse event occurring after start of study medication and within the time of residual drug effect (30 days after the last administration of the study medication), or a pre-treatment adverse event or pre-existing medical condition that worsens in intensity after start of study medication and within the time of residual drug effect.

Adverse events should be recorded as diagnoses, if available. If not, separate sign(s) and symptom(s) are recorded. One diagnosis/symptom should be entered per record.

Note that death is not an adverse event but the cause of death is. An exception is the adverse event of sudden death of unknown cause. Note that hospitalization is not an adverse event; however, the reason for hospitalization is. Procedures are not adverse events; the reasons for conducting the procedures are. In general, only the reason for conducting the procedure will be captured as an adverse event. However, if deemed necessary by the PI, a procedure can be captured along with the reason for conducting the procedure.

An overdose or medication error is not an adverse event unless it is temporally associated with an unfavorable or unintended sign or symptom.

While pregnancy in and of itself is not a SAE, for the purposes of this trial, should a pregnancy occur in a subject or subject's partner, it should be reported on a Pregnancy Reporting form within 24 hrs of being aware and be followed until an outcome is received.

7.3.1.1 Serious Adverse Events

Each AE is to be classified by the PI as serious or non-serious. A serious adverse event (SAE) is any untoward medical occurrence or effect that occurs at any dose:

- Results in death
- Is life-threatening (*i.e.*, an immediate risk of death)
- Requires in-patient hospitalization or prolongation of existing hospitalization
- Results in persistent or significant disability/incapacity
- Is associated with a congenital anomaly/birth defect
- Is an important medical event.

An adverse event caused by an overdose or medication error is considered serious if a criterion listed in the definition above is fulfilled.

Important adverse events that may not result in death, may not be life-threatening, or do not require hospitalization may be considered serious when, based upon appropriate medical judgment, they may jeopardize the patient's safety or may require medical or surgical intervention to prevent one of the outcomes listed above.

Serious adverse events also include any other event that the PI or Sponsor judges to be serious or which is defined as serious by the regulatory agency.

The PI is to report all directly observed adverse events and all adverse events spontaneously reported by the trial patient using concise medical terminology.

7.3.1.2 Procedures for Assessing, Recording, and Reporting Adverse Events and Serious Adverse Events

Throughout the duration of the study, the PI will closely monitor each patient for evidence of drug intolerance and for the development of clinical or laboratory evidence of adverse events. All AEs (expected or unexpected) which occur during the course of the study, whether observed by the PI or by the patient, and whether or not thought to be drug-related, will be reported and followed until resolution or until they become stable.

The description of the AE will include description of the event, start date, stop date, intensity, if it was serious, relationship to test drug, change in test drug dosage, if the patient died, and if treatment was required. Events will be recorded as one of the following severity/causality categories below (CTCAE v5.0):

Severity	Definition
Mild (Grade 1)	Asymptomatic or mild symptoms, clinical or diagnostic observations only; intervention not indicated
Moderate (Grade 2)	Minimal, local or noninvasive intervention indicated; limiting age-appropriate instrumental ADL (e.g., meal preparation, shopping, using telephone, managing money, etc.)
Severe (Grade 3)	Medically significant but not immediately life-threatening; prolongation of hospitalization indicated; disabling; limited self-care (e.g., bathing, dressing, feeding self, using toilet, etc.)
Very severe (Grade 4)	Life-threatening consequences; urgent intervention indicated
Death (Grade 5)	Death related to AE

Category	Definition
Unrelated	Clearly and incontrovertibly due only to extraneous causes and does not meet criteria listed under possible or probable.
Unlikely	Does not follow a reasonable temporal sequence from administration. May have been produced by the patient's clinical state or by environmental factors or other therapies administered.
Possible	Follows a reasonable temporal sequence from administration but may have been also produced by the patient's clinical state, environmental factors or other therapies administered.
Probable	Clear-cut temporal association with administration with improvement on cessation of investigational medicinal product or reduction in dose. Reappears upon rechallenge. Follows a known pattern of response to the investigational medicinal product.
Definitely	There is evidence of exposure to the test product, for example, reliable history or acceptable compliance assessment; the temporal sequence of the AE onset relative to the drug is reasonable; the AE is most likely to be explained by the drug treatment than by another cause; the challenge is positive; re-challenge (if feasible) is positive; the AE shows a pattern consistent with previous knowledge of the drug treatment.

Adverse events with the causality assessed as possible, probable, and definitely are categorized as related to study medication and are called adverse drug reactions.

7.3.1.2.2 Fatal or Life-threatening Serious, Unexpected Adverse Drug Reactions

The Sponsor or designate is responsible for notifying regulatory agencies of fatal or life-threatening serious, unexpected adverse drug reactions (by telephone, facsimile transmission or in writing) as soon as possible, but no later than 7 calendar days after becoming aware of the information. Additionally, within 8 days after having informed the agency(ies), a complete report must be submitted, including an assessment of the importance and implication of any findings. Syneos Health Canada will handle notifications to the Canadian regulatory agency on behalf of the Sponsor.

It is the responsibility of the clinical site to report as soon as possible, but no later than 7 calendar days after first knowledge by the Investigator, fatal or life-threatening serious, unexpected adverse drug reactions to the Independent Ethics Committee (IEC) responsible for the study.

7.3.1.2.3 Other Suspected, Unexpected, Serious Adverse Drug Reactions (SUSAR)

The Sponsor is responsible for notifying regulatory agencies of all other suspected, unexpected, serious adverse drug reactions that are neither fatal nor life-threatening as soon as possible, but no later than 15 calendar days after becoming aware of the information. Syneos Health Canada will handle notifications to the Canadian regulatory agency on behalf of the Sponsor.

7.3.2 Other Assessments

7.3.2.1 Clinical Laboratory Tests (Appendix 2)

- Hematology Complete blood count: total white blood cell count with differential (neutrophils, lymphocytes, monocytes, eosinophils, and basophils), total red blood cells (RBC, hemoglobin [Hgb], hematocrit, mean corpuscular volume, mean corpuscular Hgb, and mean corpuscular Hgb concentration), and platelets.
- Biochemistry Sodium, potassium, glucose, blood urea nitrogen, chloride, creatinine and eGFR, calcium, bilirubin (total), alkaline phosphatase, aspartate transaminase, alanine

transaminase, gamma-glutamyl transferase, total protein, albumin, and carbon dioxide (CO₂).

- Coagulation Activated Partial Thromboplastin Time (aPTT), Prothrombin time (PT), International Normalized Ratio (INR), and activated clotting (or coagulation) time (ACT), the latter only if part of SOC at the investigational site.
- Urinalysis Dipstick for presence of blood, glucose, ketones, and protein; pH, color (if applicable), transparency, specific gravity, and urobilinogen.

Blood and urine samples will be obtained at Screening, and prior to the drug infusion on Days 3, EOT, and at EOS, and as clinically indicated for evaluation of blood chemistries, hematology, coagulation, and urinalysis.

7.3.2.2 LSALT Peptide and Metabolite Pharmacokinetics

Blood samples will be drawn at Baseline prior to initiation of drug administration, at the mid-point (1 hour) of the 2-hour infusion and immediately following the end of the 2-hour infusion on Days 1, 3, and at EOT for measurement of LSALT peptide and metabolite(s) analysis (See Section 8.1 Study Flow Chart). The time of the blood sample collection and the time of the most recent dose prior to the blood sample collection will be recorded accurately on the eCRF. Samples of blood will be centrifuged to obtain plasma; refer to the Laboratory Manual for Pharmacokinetic Sample Collection.

7.3.2.3 Measurement of Cytokines and Other Biomarkers

Blood samples will be drawn at Baseline prior to initiation of drug administration, at the mid-point (1 hour) of the 2-hour infusion and immediately following the end of the 2-hour infusion on Days 1, 3, EOT, and a single blood draw at EOS for measurement of cytokines and other biomarkers (See Section 8.1 Study Flow Chart). Samples will be analyzed for the following biomarkers: IL-1 α , IL-1 β , hs-troponin, and ferritin levels, as well as other exploratory biomarkers. Please refer to the Laboratory Manual for more specific instructions.

7.3.2.4 Cardiovascular Assessments

Vital signs including supine pulse rate and blood pressure will be measured at Screening, and on Days 3, EOT, and EOS. ECGs (12-lead) will be recorded at Baseline pre-dose, Day 3, EOT, and at EOS (if clinically indicated). Highly-sensitive troponin levels will be compared from baseline and between treatment groups throughout the study (refer above to Section 7.3.2.3).

7.3.2.5 Pulmonary Assessments

Chest x-rays will be obtained at Baseline, Day 3, at time of clinical improvement, at EOT, at EOS, and where clinically indicated. All x-rays will be recorded in the eCRF. Chest CT will be obtained as per clinical practice at the study site.

8 STUDY PROCEDURES AND FLOW CHART

8.1 Study Flow Chart

Calendar	Admission ^a	Admission ^b	Treatment Period	Treatment Period	EOT	EOS
Day	1	1	1 – 14 (max)	3	Variable	28±3
Sign informed consent	X					
Assign screening number	X					
Inclusion/exclusion criteria	X					
Review demographics	X					
Review medical history	X					
Concomitant meds ^c	X		X	X	X	X
Physical exam ^c	X		X	X	X	X
Respiratory exam ^c	X		X	X	X	X
Urine pregnancy in WCBP	X					
Clinical labs/Urine tests ^{c,d}	X			X	X	X
12-lead ECG ^e	X			X	X	X
Vital signs ^{c,f}	X		X	X	X	X
eGFR ^{b,d}	X			X	X	X
SARS-CoV-2 testing swabs ^{c,g}	X			X	X	X
Chest x-ray ^h		X		X	X	X
PK and biomarker samples ⁱ		X		X	X	X
Randomization		X				
Study drug administration		X	X	X	X	X
AE assessments		X	X	X	X	X
SARS-CoV-2 IgG, IgA, IgM levels		X				X
Berlin Definition ^{j,k}		X		X	X	X
SOFA score ^{j,l}		X		X	X	X
mMRC score ^{j,m}		X		X	X	X
APACHE II score ^{j,n}		X		X	X	X
Health Outcomes						X

^a Screening to determine eligibility (prior to randomization)

^b Baseline after Screening and prior to the start of study drug unless otherwise indicated.

^c Performed at Screening, Day 3, and EOT prior to drug administration, and at EOS.

^d Hematology, biochemistry, coagulation, and urinalysis will be obtained and eGFR will be calculated (Appendix 2), and when clinically indicated.

^e 12-Lead ECG (supine) will be recorded at time 0 (pre-dose) at Screening, Day 3, EOT, and at EOS (only if clinically indicated). Also, an ECG will be obtained during the study when clinically indicated.

^f Blood pressure (supine), pulse rate (supine), body temperature, respiration rate (supine), actual body weight (kg), and height (cm). Note: Height will only be measured at Screening.

^g Swabs (nasal, throat, sputum, or lower respiratory tract) at Screening, Day 3, EOT, and EOS.

^h Chest x-rays at Baseline (Day 1), Day 3, at time of clinical improvement, at EOT, and EOS. A chest x-ray will also be obtained if clinically warranted and recorded in the eCRF.

ⁱ Blood draws at Baseline pre-dose, at the mid-point (1 hr) and at the end of 2-hr infusion of study drug on Days 1, 3, and EOT, and a single blood draw at EOS.

^j Obtained at Baseline, Day 3, when clinically indicated, at EOT, and at EOS.

^k Appendix 3

^l Appendix 4

^m Appendix 5

ⁿ Appendix 6

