 - Ulinastatin 200,000 IU or greater
 - High dose intravenous Vitamin C
 - Budesonide and formoterol
 - Bevacizumab to prevent ARDS
 - Dornase alfa to reduce hypoxemia in ventilated trauma patients.
7. As indicated in the inclusion criteria, pregnant female patients are excluded from study. Further, female patients who are nursing are excluded from study.
8. Has any medical condition considered to be clinically significant and could potentially affect patient safety or study outcome, including but not limited to:
 - Acute or chronic kidney disease (stage-4 or -5 renal impairment; eGFR <30 mL/min/1.73 m² or hemodialysis)
 - End-stage malignancy undergoing treatment
 - Immunocompromised patients or those with medical/surgical conditions (*e.g.*, solid organ transplantation) which require chronic immunosuppression

- Chronic hematologic disease which, in the opinion of the PI, prohibits the patient from entering into study
- Acute liver injury with AST and/or ALT levels greater than 3x ULN, unless recent injury (within 2 weeks) likely due to COVID-19 infection
- History of coagulopathy of unknown etiology, as defined by abnormal ACT (only if part of SOC), aPTT, and/or PT/INR values at least 2-fold outside normal limits, and currently present at screening, and/or
- End-stage lung disease, acute lung injury, very severe chronic obstructive pulmonary disease (COPD) as assessed by the GOLD criteria (GOLD Stage IV), or mechanical ventilation.

TEST PRODUCT, DOSE, AND MODE OF ADMINISTRATION:

LSALT peptide or an equivalent volume of commercially-available 0.9% sodium chloride (saline) solution to a volume of 100 mL mini-IV bag by an unblinded Pharmacist or designate. The drug will be infused into the patient through a peripheral 18, 20, or 22 g intravenous catheter over 2 hours and under the supervision of the Principal Investigator. Study drug may also be administered through a central line. Study drug will be administered once daily at a consistent time throughout the study.

DURATION OF TREATMENT: Maximum of 14 days.

DISCONTINUATION FROM TREATMENT:

Reasons for permanent discontinuation of treatment include the following:

- Patient experiences two or more Grade 2 toxicities or one or more Grade 3 or 4 toxicity considered by the PI to be associated with LSALT peptide treatment (CTCAE v5.0, 2017)
- Patient requests to discontinue treatment or patient withdrawal of consent

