Duration of therapy will be a maximum of 14 days. Patients will be maintained on the standard of care (SOC) for the treatment of COVID-19 as defined by institutional guidelines and/or physician practice. Co-morbidities and concomitant medications will be reviewed daily and documented in the patient's eCRF. The risk of venous thromboembolism (VTE), a potential consequence of SARS-CoV-2 infection, will be assessed and prophylaxis will be included as SOC for every patient (Zhai et al, 2020; Klok et al, 2020). Please refer to antithrombotic therapy in patients with COVID-19 (COVID-19 Treatment Guidelines Panel, Antithrombotic Therapy in Patients with COVID-19, p197; 17-December-2020).

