5.2 Number of Patients (Planned)

Thirty (30) patients will be randomized to active drug (LSALT peptide) and 30 patients will be randomized to matching placebo. Patients and, if necessary, the Legal Authorized Representative (LAR), the Investigational Staff, and the Sponsor and its representatives will not know the randomization schemata. The Pharmacist at the site will be unblinded and prepare drug/placebo for injection.

A Data and Safety Monitoring Board (DSMB) will evaluate patients on a continuing basis for primarily safety assessments but also the adequacy of treatment based upon clinical data of the patient, target drug concentrations, and data obtained from the AB001 PK study in healthy subjects to offer recommendations to the Sponsor. In the absence of adverse events or any safety issues during the course of study, the DSMB may recommend continuance or suspension of the study due to futility or safety issues. The DSMB will meet at least monthly if not more frequently based upon enrollment throughout the study period. Per protocol, at no time will patients be dosed for more than 14 days of therapy. The DSMB Charter will outline all processes for changes to the protocol and protocol design prior to the first patient being enrolled into study.

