5.3 Discussion of Study Design

This double-blind, placebo-controlled, proof-of-concept Phase 2 study is designed to evaluate LSALT peptide compared with placebo in a defined number of adult hospitalized patients with the diagnosis of COVID-19. This is a 1:1 randomization comparing 5 mg LSALT peptide daily with matching placebo. LSALT peptide or drug-free saline will begin immediately once the patient meets all inclusion/exclusion criteria at the start of hospitalization and followed with physical and respiratory exams, blood chemistries, coagulation, hematology, ECGs, SARS-CoV-2 tests, CXRs, biomarkers, and PK will be recorded periodically throughout the 28 day study. When clinically indicated, questionnaires (APACHE II, SOFA) will be obtained at Baseline, EOT, and EOS; venous blood gas (VBG) or HCO_3 (bicarbonate) levels may be substituted for arterial blood gas (ABG) if it is SOC or in the patient's best interest, and results in comparable APACHE II and SOFA scores (Brown *et al*, 2016). Other questionnaires (Berlin Definition and modified Medical Research Council Dyspnea Scale) will be assessed at Baseline, Day 3, EOT, and EOS. Patients will be maintained on SOC, including prophylaxis or treatment for VTE, per institutional guidelines throughout the study. Dosing will end on Day 14, or at cure or increasing severity of ARDS, or at death. Patients will be followed clinically, and safety and efficacy measures will be recorded at end of study (EOS; Day 28) or death, whichever occurs first.

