8.2.4 During Treatment Period (Day 3 and EOT, and when clinically indicated)

- Document concomitant drugs, including drug name, dose, and frequency
- Perform physical examination including respiratory exam
- Obtain chest x-ray on Day 3, in the event of clinical improvement, and at EOT, and when clinically indicated
- 12-lead ECG
- Laboratory tests including hematology, biochemistry, coagulation, and urinalysis on Day 3, EOT, and if clinically indicated
- Measure vital signs, including blood pressure (sitting), pulse rate, body temperature, respiration rate, and actual body weight (kg) daily or as clinically indicated – note: no need to document height.
- Calculate eGFR
- Administer IV drug over 2 hours
- Collect blood samples (5 mL each) at mid-point and end of the 2-hour drug infusion for PK and biomarker analysis. Prepare the samples per Section 7.3.2.2.
- Review and record any TEAEs
- Swab nasal, throat, sputum, or lower respiratory tract source for SARS-CoV-2 on Days 4, 7, 10, and 14 (if necessary).
- Complete the (1) Berlin Definition (Appendix 3), (2) SOFA score (Appendix 4), and (3) modified Medical Research Council Dyspnea Scale (Appendix 5), and (4) APACHE II score (Appendix 6; only if clinically indicated).

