8.2.5 End of Treatment (EOT)

The EOT visit refers to the completion of the last dose of study drug. All study assessments outlined during the Treatment Period are to be performed. For a complete list of assessments, refer to the Study Flow Chart.

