8.2.6 End of Study (Day 28 EOS ± 3 days)

- Document concomitant drugs, including drug name, dose, and frequency
- Perform physical examination including respiratory exam
- Laboratory tests including hematology, biochemistry, coagulation, and urinalysis, and antiviral antibodies (IgG, IgM, IgA)
- Collect blood sample in the morning for biomarker analyses. Prepare the samples per Section 7.3.2.2.
- 12-lead ECG (if clinically indicated)
- Obtain chest x-ray
- Measure vital signs, including blood pressure (sitting), pulse rate, body temperature, respiration rate, and actual body weight (kg)
- Calculate eGFR
- Review and record any TEAEs
- Swab nasal, throat, sputum, or lower respiratory tract source for SARS-CoV-2 if not eradicated on Day 14.
- Complete the (1) Berlin Definition (Appendix 3), (2) SOFA score (Appendix 4), and (3) modified Medical Research Council Dyspnea Scale (Appendix 5), and (4) APACHE II score (Appendix 6) on Day 28 (EOS).
- Record healthcare resource utilization.

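### The flow chart marks study drug administration at the Day 28 visit, while the rest of the protocol ends dosing by Day 14

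*Combined protocol and SAP*

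**What the plan says.** The flow chart in Section 8.1 has six visit columns: Screening and Baseline (both on Day 1), the treatment period (Days 1 to 14 at most), Day 3, EOT, and EOS (Day 28±3). The row "Study drug administration" is blank under Screening and has an X in each of the other five columns, including EOS. No footnote is attached to the row.

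The text elsewhere in the protocol reads as follows:

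- Synopsis: "DURATION OF TREATMENT: Maximum of 14 days".
- Section 5.1: "Duration of therapy will be a maximum of 14 days".
- Section 5.2: "at no time will patients be dosed for more than 14 days of therapy".
- Section 5.3: "Dosing will end on Day 14, or at cure or increasing severity of ARDS, or at death".
- Section 8.2.5: "The EOT visit refers to the completion of the last dose of study drug".
- Sections 8.2.2, 8.2.3 and 8.2.4, the visit lists for Baseline, the treatment days, and Day 3 with EOT: each has a dosing item, worded in 8.2.4 as "Administer IV drug over 2 hours".
- Section 8.2.6, the visit list for EOS: assessments and sample collection only, with no dosing item.

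**The concern.** A flow chart is an operative schedule. Section 8.2.5 sends the reader to this one for the full list of assessments. Taken at face value, the row calls for an infusion at a visit that every narrative section places after treatment has ended.

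The statement in Section 6.2 that drug is given once daily throughout the study does not settle the matter, because the study itself runs to Day 28.

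At stake is an unplanned exposure. It would come after the visit defined by the last dose, so the EOT date and the exposure record would no longer agree. It would also move the end of adverse event collection, which Section 7.3.1 ties to the final dose.

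**Working it through.** There is no planned statistical figure to reproduce. The check is a comparison of passages plus simple day counts.

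**1. Is the row displaced?** The row has five marks for the five columns after Screening. A sideways shift would move marks without adding one. Nearby rows keep their blanks: randomization is marked only at Baseline, the antibody row only at Baseline and EOS, and health outcomes only at EOS. The study drug row has the same pattern as the adverse event row directly below it, where an EOS mark is expected. A row copied in error would explain this, but the documents do not show that it happened.

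**2. The passages side by side**

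| Source | Dosing at EOS? |
|---|---|
| 8.1, study drug row | Yes (X) |
| 8.1, footnote c | No: at Screening, Day 3 and EOT, procedures are timed before dosing; EOS is listed separately without that condition |
| 8.1, footnote i | No: infusion-timed draws on Days 1, 3 and EOT; one draw at EOS |
| 5.1 and 5.2 | No for a patient who has had 14 days of dosing |
| 5.3 | No: Day 14 is the latest dosing day |
| 7.2 | No infusion-timed sample at EOS |
| 8.2.5 | No: a dose after EOT contradicts the definition of EOT |
| 8.2.6 | No dosing item |

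**3. Which passages conflict for every patient.** Section 5.2 limits the number of days of therapy. After 14 daily doses, an EOS dose makes 14 + 1 = 15 dosing days, which breaches it. After 13 or fewer, the total is at most 13 + 1 = 14, and the sentence is not literally breached. Sections 5.3 and 8.2.5 conflict with the mark whatever the number of doses given.

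**4. Gap from the last permitted dosing day**

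- EOS window: 28 − 3 = Day 25 to 28 + 3 = Day 31.
- Gap from Day 14: 25 − 14 = 11 days to 31 − 14 = 17 days; on nominal Day 28 it is 14 days.
- The gap is longer for a patient whose dosing stopped before Day 14.

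**5. Adverse event window (30 days after the final dose, Section 7.3.1)**

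- Final dose on Day 14: 14 + 30 = Day 44.
- Final dose at EOS: 25 + 30 = Day 55 to 31 + 30 = Day 61.

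**6. Compliance (80% to 120%, Section 6.2.3).** The protocol does not state the denominator. Assuming 14 planned doses, 15/14 = 107%, which is inside the range. For a full-course patient, the compliance check would therefore not flag the extra dose.

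**The case against.** The strongest objection is that the point rests on one cell of a table read by a program, and the page image was not available. Other tables in the document look damaged: the SOFA liver row and the APACHE II grid are examples. Ruling out a column shift does not rule out a repeated cell, and the study drug row has no footnote to test it against. This stands as a limit on confidence, and it is why the original page should be checked first. It remains unproven, since the neighbouring rows keep their blanks.

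A second objection is that the protocol already answers the question many times over, including in the chart's treatment column heading and footnotes. That makes it unlikely that a site would dose at EOS. It does not remove the mark from the schedule.

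A reader might go further and infer any of the following, none of which the documents support:

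- *That the plan intends a Day 28 infusion.* No narrative section provides for one.
- *That Day 28 biomarkers would be contaminated.* Section 8.2.6 sets a morning draw but gives no order relative to an infusion, so an effect is possible only if blood were taken during or after it.
- *That the extra dose would always come 14 or more days after the last permitted dosing day.* The EOS window allows as few as 11.
- *That the efficacy analysis is affected.* No endpoint, sample size or test depends on this cell.

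**Conclusion.** Wrong as written, and minor. This is an internal inconsistency and not a design choice: the study drug row in Section 8.1 cannot be reconciled with Sections 5.3, 8.2.5 and 8.2.6 or with the chart's own footnotes c and i. For full-course patients it also conflicts with Sections 5.1 and 5.2.

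If the mark were followed, the consequence would be one infusion per affected patient, 11 to 17 days after Day 14 or longer after an earlier stop. For a patient last dosed on Day 14, adverse event collection would then end on Days 55 to 61 and not on Day 44. These consequences arise only at a site that follows the mark against the narrative text, which is unlikely.

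The conclusion assumes that the extracted table reproduces the page faithfully. If the original cell is blank, the point falls away.

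**What to change.** Check the EOS cell of the study drug row against the original page. If the mark is there, reconcile the row with Sections 5.1 to 5.3, 8.2.5 and 8.2.6, and with footnotes c and i, so that the chart and the text give sites one instruction. Which instruction is right is for the sponsor to state. The cost is a short edit in the next amendment or a clarification letter to sites, with no change to any analysis.
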